2. LIST OF ABBREVIATIONS

Term	Definition / description
AE	Adverse Event
ATC	Anatomical Therapeutic Chemical
BI	Boehringer Ingelheim
BP	Blood Pressure
BMI	Body Mass Index
BRPM	Blinded Report Planning Meeting
CRF	Case Report File
CT	Computer Tomography
CTP	Clinical Trial Protocol
CTR	Clinical Trial Report
DMC	Data Monitoring Committee
ECG	Electrocardiogram
EoT	End-of-Text
EX	Exclusion Criteria
FAS	Full Analysis Set
ICH	International Conference on Harmonisation
sICH	symptomatic Intracranial Haemorrhage
IN	Inclusion Criteria
IPV	Important Protocol Violation
LOCF	Last Observation Carried Forward
IV	Intravenous
MAC	Meta-Analytic-Combined
Max	Maximum
MedDRA	Medical Dictionary for Drug Regulatory Activities
Min	Minimum
MQRM	Medical Quality Review Meeting
MRI	Magnetic Resonance Imaging
mRS	Modified Rankin Scale
N	Number of Patients
NIHSS	National Institute of Health Stroke Scale
PN	Preferred Name

Term	Definition / description
PR	Pulse Rate
PT	Preferred Term
PV	Protocol Violation
Q1	Lower Quartile
Q3	Upper Quartile
REP	Residual Effect Period
SAE	Serious Adverse Event
SAS	Statistical Analysis Software
SD	Standard Deviation
sICH	symptomatic Intracranial Haemorrhage
SOC	System Organ Class
TCM	Trial Clinical Monitor
ToC	Table of Contents
TS	Treated Set
TSAP	Trial Statistical Analysis Plan
WHO-DD	World Health Organization's Drug Dictionary
WLOCF	Worst and Last Observation Carried Forward

3. INTRODUCTION

As per ICH E9 [\[1\]](#), the purpose of this document is to provide a more technical and detailed elaboration of the principal features of the analysis described in the protocol, and to include detailed procedures for executing the statistical analysis of the primary and secondary variables and other data.

This trial statistical analysis plan (TSAP) assumes familiarity with the Clinical Trial Protocol (CTP), including Protocol Amendments. In particular, the TSAP is based on the planned analysis specification as written in Section 7 of the CTP [\[2\]](#) “Statistical Methods and Determination of Sample Size”. Therefore, TSAP readers may consult the CTP for more background information on the study, e.g., on study objectives, study design and population, treatments, definition of measurements and variables, planning of sample size, randomisation.

This TSAP is also used as the interim TSAP. The interim analysis will be performed when 60 patients enter and complete the study. The safety and efficacy will be evaluated on the first 60 patients who complete the study.

SAS® Version 9.2 versions will be used for all analyses.

4. CHANGES IN THE PLANNED ANALYSIS OF THE STUDY

There has been no change in the planned analyses from the statistical methods described in the CTP.

5. ENDPOINT(S)

Please refer to Section 5.1 in CTP [\[2\]](#).

5.1 PRIMARY ENDPOINT(S)

The primary efficacy endpoint is the percentage of patients with mRS 0-1 (favourable outcome) at Visit 5 (i.e., Day 90) after stroke onset by face-to-face interview with patient. A patient is considered to be a mRS 0-1 responder (response value set to 1) if he/she obtained a response of 0 or 1 on the modified Rankin scale otherwise the response value will be set to 0.

The primary safety endpoint is the percentage of patients with symptomatic intracranial haemorrhage (sICH) centrally evaluated by DMC consultants according to ECASS III definition within the whole study period. ECASSIII definition is any apparently extravascular blood in the brain or within the cranium that was associated with clinical deterioration (defined by an increase in the National Institute of Health Stroke Scale (NIHSS) score of 4 or more points), or that led to death and that was identified as the predominant cause of the neurological deterioration.

5.2 SECONDARY ENDPOINT(S)

5.2.1 Key secondary endpoint(s)

Not applicable.

5.2.2 (Other) Secondary endpoint(s)

The percentage of global outcome responder at Visit 5 (i.e. Day 90) if he/she obtains the following results at Visit 5 (i.e. Day 90) (for all of the 4 endpoints)

mRS score of 0 to 1
Barthel Index score ≥ 95
NIHSS score of 0 to 1
Glasgow Outcome Scale score of 1

The secondary safety endpoints are:

- Patient's survival at Visit 5 (censoring at day 90)
- Frequency of deaths related to stroke or of neurological causes
- Frequency and severity of adverse events
- Incidence of cerebral herniation and symptomatic edema

6. GENERAL ANALYSIS DEFINITIONS

6.1 TREATMENT(S)

This is a single dose study. The treatment periods are defined as below:

- Screening: from the time of signing informed consent to the start time of bolus treatment administration
- On-treatment: through the drug treatment administration and residual effect period (REP, is defined as 7 days after finishing the drug medication)
- Post-treatment: after end of the REP to the Visit 5 (i.e. Day 90)
- Post-study: after Visit 5 (i.e. Day90)

Adverse events (AEs) in on-treatment period will be summarized as primary interest. The frequency of all AEs collected from signing informed consent until to Visit 5 (i.e. Day 90) will also be summarized.

6.2 IMPORTANT PROTOCOL VIOLATIONS

No per protocol analysis will be performed for this study; however patients with potential important protocol violations (IPVs) will be documented. The following list of potential IPVs will be used; note that this is a working list and may not be finalised until the final Blinded Report Planning Meeting (BRPM) prior to database lock. Inclusion criteria/exclusion criteria numbers refer to the definition given in the protocol or case report file (CRF).

Table 6.2: 1 Important protocol violations

Category / Code	Description	Comment/Example	Excluded from
A	Entrance criteria not met		
A1	Inclusion Criteria Not Met		
A1.1*	Age is greater than 80 or lower than 18	Inclusion criterion IN1 not met	None
A1.2	Women pregnant, nursing or with childbearing potential do not use highly effective methods of birth control	Inclusion criterion IN2 not met Exclusion criterion EX17 met	None
A1.3	Diagnosis of ischemic stroke without a measureable neurological deficit	Inclusion criterion IN4 not met	None
A1.4.1*	Thrombolytic therapy initiated within 3 hours of stroke onset.	Inclusion criterion IN5 not met or Exclusion criterion EX1 met	None
A1.4.2*	Thrombolytic therapy initiated beyond 4.5 hours of stroke onset.	Inclusion criterion IN5 not met or Exclusion criterion EX1 met	None
A2	Exclusion Criteria Met		
A2.1*	The time of symptom onset is unknown	Exclusion criterion EX1 met	None
A2.2	Evidence of intracranial haemorrhage on the CT/MRI-scan or symptoms suggestive of subarachnoid haemorrhage, even if the CT/MRI-scan is normal	Exclusion criterion EX2 met	None
A2.3	Patients who must or wish to continue the intake of restricted medications (see protocol section 4.2.2.1) or any drug considered likely to interfere with the safe conduct of the trial	Exclusion criterion EX3 met	None
A2.4	Acute bleeding diathesis (detailed items can be found in CRF)	Exclusion criterion EX4 met	None
A2.5	Bacterial endocarditis, pericarditis, acute pancreatitis, or severe hepatic dysfunction, including hepatic failure, cirrhosis, portal hypertension (oesophageal varices) and active hepatitis	Exclusion criterion EX5, EX6 or EX7 met	None
A2.6	Significant trauma or major surgery (according to the investigator's assessment) in past 3 months	Exclusion criterion EX8 met	None
A2.7	Severe stroke as assessed clinically (e.g. NIHSS>25) and/ or imaging demonstrates multi-lober infarction (hypodensity >1/3 cerebral hemisphere)	Exclusion criterion EX9 met	None
A2.8	Symptoms rapidly improved significantly before start of study drug	Exclusion criterion EX10 met	None
A2.9	Severe uncontrolled arterial hypertension	Exclusion criterion EX11 met	None
A2.10*	Serious abnormal blood glucose	Exclusion criterion EX12 met	None
A2.11*	Any history of prior stroke in previous 3 months, or any history of prior stroke with concomitant diabetes	Exclusion criterion EX13 met	None
A2.12	Seizure at stroke onset	Exclusion criterion EX14 met	None

	A2.13	Known hypersensitivity to active substance alteplase, gentamicin (a trace residue from the manufacturing process) or to any of the excipients	Exclusion criterion EX15 met	None
	A2.14	Currently enrolled in another investigational device or drug study, or less than 30 days since ending another investigational device or drug study(s), or receiving other investigational treatment(s)	Exclusion criterion EX16 met	None
B		Informed consent		
	B1	Informed consent not available /not done	e.g. date of informed consent missing No signature on ICF Detected automatically/manually	All
	B2	Informed consent too late	e.g. date of informed consent for the study not obtained prior to any study related procedure	None
C		Non compliance		
	C1	Patients not treated as label instructed	e.g. bolus date missing	None
D		Concomitant medication		
	D1	Prohibited medication use	Concomitant medications for prohibited medication use. Refer to Section 4.2.2 of the CTP.	None
E		Trial specific		
	E1	Non-stroke patient	e.g. Lyme disease	None

* IPVs will be identified programmatically; others will be manually recorded.

6.3 PATIENT SETS ANALYSED

The treated set (TS) includes all enrolled patients who received alteplase (rt-PA) treatment at any dose. The full analysis set (FAS) is the same as TS since all treated patients will be evaluated.

All safety and efficacy analysis will be performed on the TS.

6.5 POOLING OF CENTRES

Not applicable.

6.6 HANDLING OF MISSING DATA AND OUTLIERS

According to CTP, all efforts should be made to collect complete CRF information referring to all patients with drug administration. No missing values regarding vital status and intracranial bleeds are expected.

The missing values related to efficacy outcome parameters will be imputed according to the rules described below and listed in Table 6.6:1.

Baseline imputation

In case of missing data for baseline NIHSS, the baseline NIHSS will be imputed to the best possible score (0).

Post baseline imputations

WLOCF: Worst and last observation carried forward

- any missing data that is not due to death will be replaced by the last observation carried forward (LOCF) i.e., either Visit 4, Visit 3, Visit 2, Visit 1C, Visit 1B.
- if the missing data is due to death, the data will be replaced by the worst score: the highest possible score (42) for the NIHSS, the score of 6 (i.e. Dead) for the modified Rankin scale, the score of 5 (i.e. Dead) for the Glasgow outcome, the lowest score (0) for the Barthel index.

- if the patient status (i.e. alive yes/no) is missing, the data will be replaced by the worst score excluding death: the highest possible score (42) for the NIHSS, the score of 5 for the modified Rankin scale, the score of 4 for the Glasgow outcome, the lowest possible score (0) for the Barthel index.

When all post baseline measurements are missing, the imputation across visits will depend on survival status (dead/missing/alive, alive will be handled the same as missing in this scenario) as per definition above. These imputations will be used for the derived endpoints (e.g. dichotomized endpoint) as defined in [Section 5](#).

For multi items scales (NIHSS, Barthel index): Imputation will be performed in two steps:

- 1.) Individual items will be imputed following the LOCF or worst score
- 2.) Total score is calculated

When all post baseline measurements are missing, the individual values for post baseline measurements will stay missing and the imputation across visits will depend on survival status (dead/missing/alive, alive will be handled the same as missing in this scenario) as per definition above.

In case of NIHSS missing at baseline and at all post baseline time points, then the individual values for post baseline measurements will stay missing and the total NIHSS score for all post baseline data will be imputed depending on survival status (dead/missing/alive, alive will be handled the same as missing in this scenario).

Barthel index is present only at Visit 4 and Visit 5. In case of missing items for the Barthel index at Visit 4, the worst value will be imputed for these items.

Furthermore, in cases where one of more individual items is missing, the total score must be set to missing for the observed case type of analysis.

Table 6.6:1 Handling of missing data

Endpoint	Baseline value	Baseline imputation value	Post-baseline value at visit	Patient dead/alive at visit	Post baseline imputation value at visit
modified Rankin scale			Available	Alive	NA
			Missing	Alive	LOCF or worst excluding death (5) if missing at Visit 4
			Missing	Dead	Worst (6)
			Missing	Missing	Worst excluding death (5)
Barthel Index			Available	Alive	NA
			Missing	Alive	LOCF or worst if missing at Visit 4
			Missing	Dead	Worst (0)
			Missing	Missing	Worst (0)
Glasgow outcome			Available	Alive	NA
			Missing	Alive	Worst excluding death (4)
			Missing	Dead	Worst (5)
			Missing	Missing	Worst excluding death (4)
NIHSS total score	Available or missing	If missing impute best value (0)	Available	Alive	NA
	Available or missing	If missing impute best value (0)	Missing	Alive	LOCF or worst (42) if all post-baseline were missing
	Available or missing	If missing impute best value (0)	Missing	Dead	Worst (42)
	Available or missing	If missing impute best value (0)	Missing	Missing	Worst (42)

NIHSS Total score:

The total score of the NIHSS is the sum of the **15** individual item scores: level of consciousness (1), LOC questions (2), LOC commands (3), best gaze (4), visual (5), facial paresis (6), motor arm right (7), motor arm left (8), motor leg right (9), motor leg left (10), limb ataxia (11), sensory (12), best language (13), dysarthria (14), extension and inattention (15).

For the calculation of the total score:

The scores of '9' on motor (7-10) indicating amputation or joint fusion on motor arm right or left, motor leg right or left will be replaced by (4) for post baseline value and by best case (0) at baseline.

A score of '9' on dysarthria (14) will be replaced by the worst case value (2) for post baseline value and by best case (0) at baseline.

This rule is to be applied for observed cases and WLOCF.

The censoring rules for time to death (survival time, [day]) at Day 90 and censoring flag will be calculated as following manner:

➤ **for a dead patient:**

death=yes

censoring flag=0

survival time=date of death – date of start bolus +1

if survival time >90 (patient alive at Visit5)

then death=no, censoring flag=1, survival time=90

➤ **for patient alive at Visit 5:**

death=no

censoring flag=1

survival time= date of last contact – date of start bolus +1

if survival time>90 then survival time=90

➤ **for a lost to follow up patient:**

death = no

censoring flag=1

if « last date patient known to be alive » is known

then survival time= last date patient known to be alive – date of start bolus +1

if « last date patient known to be alive » is unknown

then survival time= date of last contact – date of start bolus +1

if survival time>90 then survival time=90

Date of last contact is the maximum of {date of last measurement or visit, date of trial completion, last available date from AE and last available date from CM}.

The censoring rules for time to death (survival time, [day]) overall study and censoring flag will be calculated as following manner:

All deaths are taken into account whatever their time of occurrence, and even if they occurred after the 97 days (90 days +7).

➤ **for a dead patient:**

death=yes
censoring flag=0
survival time=date of death – date of start bolus +1

➤ **for patient alive at Visit 5:**

death=no
censoring flag=1
survival time= date of last contact – date of start bolus +1

➤ **for a lost to follow up patient:**

death = no
censoring flag=1
if « last date patient known to be alive » is known
 then survival time= last date patient known to be alive – date of start bolus +1
if « last date patient known to be alive » is unknown
 then survival time= date of last contact – date of start bolus +1

Date of last contact is the maximum of {date of last measurement or visit, date of trial completion, last available date from AE and last available date from CM}.

The length of stay in hospital will be calculated as follows:

The length of stay in hospital is expressed in days and is equal to the date of discharge date and time is approximated to 23h O'clock for the end of day minus the date and time of the start of bolus. Because the date in SAS are expressed in seconds, the results will be divided by 86400 (24*60*60) in order to obtain a results expressed in number of days. The exact time of day of when the discharge time occurred is fixed at 23H59 PM for all patients (exact time not recorded in CRF).

Example: Start of bolus: 23/01/03 12H00 and date of discharge: 30/01/03

The length of stay in hospital will be: date of discharge (30/01/03, 23H59) - date of bolus (23/01/03, 12H00) / 86400 = 7.5 days.

Missing or incomplete AE onset dates are imputed according to BI standards [27, 27].

Missing or incomplete concomitant therapy onset dates are also imputed referring to AE standards. The end dates of missing or incomplete AE and concomitant therapy will be not imputed.

Trial completion is defined as the patients who are treated and completed Day 90 visit (i.e. Visit 5).

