#### **3.3.2 Inclusion criteria**

1. Age  $\geq 18$  years at screening (visit 1A) but  $\leq 80$  years
2. Male or female patients. Women of childbearing potential must be ready and able to use highly effective methods of birth control per ICH M3 (R2) that result in a low failure rate of less than 1% per year when used consistently and correctly. A list of contraception methods meeting these criteria is provided in the patient information
3. Signed and dated written informed consent in accordance with GCP and local legislation prior to admission to the trial
4. Diagnosis of ischemic stroke with a measurable neurological deficit on National Institute of Health Stroke Scale (NIHSS)

Stroke symptoms should have been present for at least 30 minutes without significant improvement prior treatment

5. Thrombolytic therapy can be initiated within 3 to 4.5 hours of stroke onset
6. Willingness and ability to comply with protocol

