#### **3.3.3 Exclusion criteria**

1. Stroke onset  $>4.5$  hours prior to infusion start or when time of symptom onset is unknown

2. Evidence of intracranial haemorrhage (ICH) on the CT/MRI-scan or symptoms suggestive of subarachnoid haemorrhage, even if the CT/MRI-scan is normal
3. Patients who must or wish to continue the intake of restricted medications (see [section 4.2.2.1](#)) or any drug considered likely to interfere with the safe conduct of the trial
4. Acute bleeding diathesis, including but not limited to
  - a. Known genetic predisposition to bleeding or significant bleeding disorder at present or within the past 6 months
  - b. Administration of heparin within the previous 48 hours and aPTT exceeding the upper limit of normal for laboratory
  - c. Platelet count of below 100,000/mm^3
  - d. Taking oral anticoagulant
  - e. Any history of central nervous system damage (i.e. neoplasm, aneurysm, intracranial or spinal surgery)
  - f. Recent traumatic external heart massage, obstetrical delivery, within the past 10 days, recent puncture of a non-compressive blood-vessel (e.g subclavian or jugular vein puncture)
  - g. Known history of suspected intracranial haemorrhage or suspected subarachnoid haemorrhage from aneurysm
  - h. Neoplasm with increased hemorrhagic risk
  - i. Documented ulcerative gastrointestinal disease during the last 3 months, oesophageal varices, arterial-aneurysm, arterial/venous malformations
  - j. Any known disorder associated with a significant increased risk of bleeding
5. Bacterial endocarditis, pericarditis
6. Acute pancreatitis
7. Severe hepatic dysfunction, including hepatic failure, cirrhosis, portal hypertension (oesophageal varices) and active hepatitis
8. Significant trauma or major surgery (according to the investigator's assessment) in past 3 months
9. Severe stroke as assessed clinically (e.g. NIHSS>25) and/ or imaging demonstrates multi-lobar infarction (hypodensity >1/3 cerebral hemisphere)
10. Minor neurological deficit or symptoms rapidly improving before start of infusion
11. Severe uncontrolled arterial hypertension, e.g. systolic blood pressure>185 mmHg or diastolic blood pressure>110mmHg, or aggressive management (IV medication) necessary to reduce BP to these limits
12. Blood glucose <50 mg/dL or >400 mg/dL
13. Any history of prior stroke in previous 3 months, or any history of prior stroke with concomitant diabetes
14. Seizure at stroke onset

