### **National Institutes of Health Stroke Scale (NIHSS)**

The NIHSS will be recorded, if it had been collected at the time of qualifying (index) stroke. In patients, where NIHSS has not been done at the time of index stroke, it will be performed at study entry (at Visit 1). It is a tool used by healthcare providers to objectively quantify the impairment caused by a stroke. The NIHSS is composed of 11 items, and for each item a score of 0 typically indicates normal function in that specific ability, while a higher score is indicative of some level of impairment. The individual scores from each item are summed in order to calculate a patient's total NIHSS score. The maximum possible score is 42, with the minimum score being a 0. Clinical outcome will also be assessed by NIHSS scoring at 2 hours, 24 hours, and on day 7, 30 and 90.

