6.7 BASELINE, TIME WINDOWS AND CALCULATED VISITS

The table below presents the visit structure according to the study flowchart depending on the time window scheduled in the CTP.

Table 6.7: 1 Visit structure

Period	Baseline	Trial drug admin.	On-treatment & Post-treatment					
Visit number per protocol	V1A		V1B#	V1C#	V2	V3	V4	V5
Planned study window	-4.5-0 hour	↔x→ 60 mins	1 hour ± 15 mins	2 hrs ± 30 mins	24 hrs ± 2hr	7 days ± 3 day	30 days ± 3 days	90 days ± 7 days
Study Day	← D0 →			D1	D7	D30	D90	
Visit description*	Baseline		Day0 (1H)	Day0 (2 H)	Day1	Day7	Day30	Day90

*label to be used in tables.

‘Baseline’ is defined as from enrolled in this study to the start time of bolus treatment administration

‘Study Day’ is calculated from the date & time of starting bolus treatment administration.

date & time is calculated from the date & time of starting infusion treatment administration.

Start of treatment:

The start of treatment (used for survival start time, length of stay in hospital, treatment at onset for adverse event) will be the **start of bolus treatment administration**; end of treatment is the end of infusion/drug/treatment administration.

Baseline value:

The baseline value will be the value recorded at V1A (last available value before the start of bolus treatment).

Change from baseline:

The change from baseline for any efficacy or safety endpoints (Vital signs) will be calculated as: value after baseline – value at baseline (V1A).

All efficacy analyses will be based on ‘nominal visits’ (CRF raw data visit) which will be labelled as indicated in the ‘Visit description’ row in tables, listings and graphs.

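### SAP 6.6 imputes a missing baseline NIHSS as 0, a total no eligible patient can have, so any summary that uses it understates severity and hides improvement

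*SAP*

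**What the plan says.** The baseline rule in SAP 6.6 is: "In case of missing data for baseline NIHSS, the baseline NIHSS will be imputed to the best possible score (0". Table 6.6:1 gives the same instruction in all four NIHSS rows: "If missing impute best value (0". The introduction to 6.6 directs its rules at missing values of efficacy outcome parameters, and SAP section 7 then applies the 6.6 imputations to the planned analyses in general.

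SAP 6.7 supplies the calculation in which a baseline value would matter. It begins "The change from baseline for any efficacy or safety endpoints (Vital signs) will be calculated as" and goes on to define change as the later value minus the Visit 1A value.

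On eligibility, Protocol 3.3.2 (criterion 4) requires "Diagnosis of ischemic stroke with a measurable neurological deficit on National Institute of Health Stroke Scale (NIHSS". Protocol 3.3.3 excludes "Minor neurological deficit or symptoms rapidly improving before start of infusion" (criterion 10) and, at the other end, "Severe stroke as assessed clinically (e.g. NIHSS>25" (criterion 9). Protocol 5.2 explains the scale. For each item, "a score of 0 typically indicates normal function in that specific ability", and for the total, "The maximum possible score is 42, with the minimum score being a 0".

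**The concern.** The imputed value describes a treated stroke patient as neurologically normal before treatment. SAP Table 6.2:1 lists a patient without a measurable deficit as a potential important protocol violation (A1.3). The imputation rule therefore gives an otherwise eligible patient the score of an ineligible one.

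Two descriptive results could be distorted:

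- **Baseline severity.** This is a single-arm trial judged against a fixed 40% response rate (Protocol 7.2), so a reader needs an accurate picture of case-mix to interpret the observed rate. Protocol 2.3 itself cites baseline NIHSS as an independent predictor of sICH (odds ratio 1.13).
- **Change in NIHSS.** With a baseline of 0, post-baseline minus baseline can never be negative, so no improvement can be recorded for that patient.

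**Working it through.** **Plan figures reproduced**

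- *NIHSS maximum.* Summing the 15 item maxima in Protocol Appendix 10.1 gives 3+2+2 (items 1a to 1c) + 2 (gaze) + 3 (visual) + 3 (face) + 4+4+4+4 (limbs) + 2 (ataxia) + 2 (sensory) + 3 (language) + 2 (dysarthria) + 2 (extinction) = 42. This matches Protocol 5.2. The minimum of 0 requires every item to be 0.
- *Power (Protocol 7.7).* With n = 120, p0 = 0.40, p1 = 0.55 and two-sided alpha 0.05, power = Φ[(0.15·√120 − 1.96·√(0.40·0.60)) / √(0.55·0.45)] = Φ[(1.643 − 0.960)/0.497] = Φ(1.373) = 91.5%. This matches Table 7.7:1. Baseline NIHSS does not enter the formula.

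**Step 1: can 0 be an eligible baseline?** A measurable deficit on the NIHSS means a total of at least 1. Exclusion 10 removes minor deficits as well, without giving a score. Exclusion 9 gives NIHSS above 25 as an example of severe stroke. The eligible range used below is therefore 1 to 25, and 0 lies outside it.

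**Step 2: error in change.** Let B be the true baseline and Y the later score.

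- True change = Y − B.
- Change under the rule = Y − 0 = Y.
- Error = Y − (Y − B) = B.

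| True baseline | Later score | True change | Change under the rule |
|---|---|---|---|
| 10 (assumed) | 3 | −7 | +3 |
| 10 (assumed) | 0 | −10 | 0 |

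Over all whole-number pairs with B from 1 to 25 and Y below B, there are 1+2+…+25 = 325 improving pairs. Of these, 25 have Y = 0 and become no change. The other 300 (92.3%) become worsening. None is recorded as an improvement. These are counts of possible score pairs, not expected patient frequencies.

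Table 6.6:1 also assigns 42 to a living patient with every post-baseline score missing. If the baseline is missing too, the computed change is 42 − 0 = +42 with nothing measured.

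**Step 3: shift in mean baseline.** If m of 120 patients are imputed and their mean true baseline is B, the shift is −m·B/120. The documents give neither m nor B, so both are assumed.

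| Imputed patients | B = 8 | B = 12 |
|---|---|---|
| 1 | −0.07 | −0.10 |
| 3 | −0.20 | −0.30 |

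With B from 4 to 15 and m from 1 to 12, the shift runs from −0.03 (1·4/120) to −1.5 (12·15/120).

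**Step 4: where the imputed 0 can travel.** The primary endpoint (mRS 0–1) and the global outcome, including its NIHSS 0–1 component, use Visit 5 values (SAP 5.1 and 5.2.2). The carry-forward rule in SAP 6.6 draws only on Visits 1B to 4, never on Visit 1A. The imputed 0 therefore cannot reach either endpoint. In the visible plan it could enter only a baseline summary or a change score.

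**The case against.** **The case is nearly empty.** NIHSS is performed at Visit 1A (Protocol 6.2.1) and underlies eligibility. Protocol 8.3.1 says that missing supporting records do not make a patient eligible. This stands as a limit on size. The SAP nonetheless provides for the case, and the value it assigns is still wrong.

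**No visible analysis uses it.** No NIHSS change endpoint appears in the public text, the parenthesis in SAP 6.7 names only vital signs, and SAP 7.1 promises descriptive statistics without naming NIHSS. Section 6.6 also speaks of efficacy outcome parameters, so it is unclear whether a baseline table would take the imputed value. This stands too, and both effects are therefore conditional. Some SAP text is not public, so use elsewhere can be neither confirmed nor excluded.

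**It is conservative.** A best-case baseline with a worst-case follow-up works against the drug. That can justify a worst-case outcome score, but not recording a stroke patient as having had no deficit.

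**Zero is not always impossible.** The treated set keeps patients who breach eligibility (A1.3 excludes from nothing), so a genuine 0 could occur there. If the item-by-item imputation in 6.6 extends to baseline, which the text leaves unclear, one missing item set to 0 could still give a plausible total, understated only by that item's true score. For observed-case analyses, a total with any missing item is set to missing. These points narrow the finding to an eligible patient whose baseline total is missing.

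**A stronger reading.** A reader might infer that false rises of 4 or more points would feed the sICH endpoint. The documents do not support this. Protocol 5.3.1 has sICH judged by the investigator and then by the DMC consultants, and nothing says that either works from imputed scores.

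**Conclusion.** The point holds as a defect in a stated rule, of minor consequence. For an eligible patient with no baseline NIHSS total, the SAP assigns a value the eligibility criteria rule out. Wherever that value is used, baseline severity is too low and change is too high by the patient's true baseline.

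The size depends on two quantities the documents do not give: the number of missing baselines, expected to be few, and the true scores, assumed here to be 8 to 12. On that basis the effect on the mean baseline is tenths of a point or less for one to three patients. For an individual patient's change score it is enough to reverse the sign.

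A reader might infer that the trial's efficacy result or its power is compromised. Neither is, because neither uses baseline NIHSS. A reader might also infer that a planned NIHSS change analysis is biased. That would follow only if such an analysis exists, and none is visible.

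**What to change.** Delete the baseline imputation paragraph from SAP 6.6 and the corresponding entries in the NIHSS rows of Table 6.6:1. Replace them with a statement along these lines: baseline NIHSS is reported as observed, with the number missing shown, and patients without a baseline NIHSS are omitted from any summary of NIHSS change from baseline. The post-baseline rules can stay as they are.

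The cost is about two lines of SAP text and a slightly smaller N in those summaries. No endpoint in the public text loses data. The sponsor should check whether any analysis in the non-public parts of the SAP relies on a complete baseline NIHSS.
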